12.1 General Aspects of Analysis

12.1.1 Sample Size

The rate of PAD and CLI within the population seen at a typical vascular clinic is estimated from prior investigation (i.e WIRB #1177294). In this previous study, 100 limbs were assessed using the ABI and graded using the Rutherford classification scheme. PAD (diagnosed via ABI score of <0.9) was present in 63% of limbs. CLI (estimated as having a Rutherford category of ≥ 4) occurred in 15% of limbs. FlowMet-R data was also collected from the above limbs, and the data analysis techniques used in the data analysis section below were applied to build a diagnostic model for PAD and CLI. ROC curves were then generated for the diagnosis of both Claudication and CLI. The resulting area under the curve (AUC) for these ROC curves was 0.67 and 0.80, respectively. However, the Claudicant group AUC had a tighter confidence interval due to larger sample size (84 vs. 22).

Using a conservative estimation that the AUC for distinguishing PAD groups from healthy controls remains within ± 0.05 of the Claudicant group, and ± 0.2 of the CLI group, an estimate for the necessary sampling size can be determined. A standard type I error rate (α) of 0.05 and power of 0.8 is desired, thus the following approximate sample size was calculated for statistically significant results [32, 33]: 160 control limbs and 240 limbs with PAD, of which at least 54 limbs with Claudication and at least 100 limbs with CLI. Limbs with CLI may be included as a subset of limbs with PAD. A minimum of 250 patients (400 limbs) and maximum of 400 patients will be enrolled in the study.

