It is well established in the literature and in clinical practice that diminished blood flow to the extremities, as a result of peripheral artery disease (PAD) or otherwise, may impair wound healing and overall tissue viability [1-5]. PAD is labeled a “large personal, social, and economic burden in the United States” by the American Heart Association and American College of Cardiology. PAD is estimated to affect 8-10 million in the United States alone, while having a significant mortality rate (30% mortality in 5 years) [6, 7]. Over \$5B is spent annually treating peripheral vascular patients, the majority of which results from late diagnoses, ineffective interventions, and resulting lower limb amputations [8].

One end-stage manifestation of PAD is critical limb ischemia (CLI) [9, 10]. Generally, CLI is defined as: "any patient with chronic ischemic rest pain, ulcers, or gangrene attributable to objectively proven arterial occlusive disease" [9]. Early detection and treatment has the potential to keep PAD from reaching the point of CLI. Angiography is the gold standard for anatomical visualization of blood vessel structure and stenosis. However, angiographic information does not provide simple and functional metrics of blood flow, especially in the case of multiple stenoses. As such, the relationship between extremity blood flow and PAD/CLI cannot be elucidated without a more appropriate methodology for quantifying peripheral perfusion.

The ankle brachial index (ABI) is perhaps the most widely used screening technique to diagnose PAD. While the ABI is relatively simple to perform, it is a ratio of systolic blood pressures rather than a direct measurement of blood flow, and, despite its widespread usage, is only a proxy of direct perfusion measurements. Generally, a cutoff of ABI less than 0.91 is used to predict the presence of PAD, and a cutoff of ABI less than 0.4 is used to predict the presence of severe PAD indicating CLI [11].

While the noninvasive technologies mentioned above are considered standard of care in vascular medicine, there remains a lack of simple and continuous methods to assess PAD severity. A portable technology capable of quantifying disease severity simply and in real time could significantly ameliorate diagnosis, surgical treatment, and follow up care.

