4.1.1.1.1 Definitions of PAD and CLI

- Two types of positive diagnosis of PAD will be explored according to published literature: (1) $ABI \leq 0.9$ or $ABI > 1.4$ and secondary verification of $TBI \leq 0.7$ with exhibition of at least mild claudication (Rutherford Category > 0), or (2) $ABI \leq 0.9$ or $ABI > 1.4$ and secondary verification of $TBI \leq 0.7$ without exhibition of symptoms. In either case, if the patient displays normal ABI but PAD is suspected, then a postexercise ABI will be performed using a 1-minute treadmill test or heel-raises. A postexercise drop of $ABI \geq 20\%$ or pressure drop $\geq 30\text{mmHg}$ will be considered a positive diagnosis [12].
- A positive diagnosis of CLI will be defined by exhibition of chronic rest pain and active wounds, verified by $TBI < 0.3$.
- Patients that are enrolled in the PAD positive cohort but are not positively diagnosed for PAD using the above definition (either because their disease is improving or they were screened incorrectly) will be considered PAD negative (see Section 7.11 for change to planned analysis).

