5.6 Exclusion Criteria

Candidates for this study who meet any of the following criteria at the time of the baseline visit are not eligible to be enrolled in this study:

PAD Positive Cohort Exclusion

- Subject is under 40 or unable to consent.
- Subject has any medical condition, which, in the judgment of the Investigator and/or designee, makes the subject a poor candidate for the investigational study.
- Subject is excluded from analysis if no stenosis is found during Doppler but Tibial disease is suspected and Tibial ultrasound is not able to be performed.
- Subject does not have a suitable finger to attach the FlowMet-R probe.
- Subject does not have a suitable 1st or 2nd digit to attach FlowMet-R probe on the limb of interest.
- Subject has undergone revascularization within the last 90 days
- Subject cannot lay safely in a supine position.

Healthy Cohort Exclusion

- Subject is under 40 or unable to consent.
- Subject has any medical condition, which, in the judgment of the Investigator and/or designee, makes the subject a poor candidate for the investigational study.
- One or more limbs has a prior or current diagnosis of PAD, or is reasonably suspected of having a diagnosis of PAD.
- Subject does not have a suitable finger to attach the FlowMet-R probe.
- Subject does not have a suitable 1st or 2nd digit to attach FlowMet-R probe.
- Subject has undergone revascularization within the last 90 days

6. Determination of Sample Size

The rate of PAD and CLI within the population seen at a typical vascular clinic is estimated from a prior investigation. In that study, 100 limbs were assessed using the ABI and graded using the Rutherford classification scheme. PAD (diagnosed via ABI score of <0.9) was present in 63% of limbs. CLI (estimated as having a Rutherford category of ≥ 4) occurred in 15% of limbs. FlowMet-R data was also collected from the above limbs, and the data analysis techniques used in the data analysis section below were applied to build a diagnostic model for PAD and CLI. ROC curves were then generated for the diagnosis of both Claudication and CLI. The resulting area under the curve (AUC) for these ROC curves was 0.67 and 0.80, respectively. However, the Claudicant group AUC had a tighter confidence interval due to larger sample size (84 vs. 22, respectively).

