Using a conservative estimation that the AUC for distinguishing PAD groups from healthy controls remains within $+/ - 0.05$ of the Claudicant group, and $+/ - 0.2$ of the CLI group, an estimate for the necessary sampling size can be determined. A standard type I error rate (α) of 0.05 and power of 0.8 is desired, thus the following approximate sample size was calculated [13,14]: 160 control limbs and 240 limbs with PAD, of which at least 54 limbs with Claudication and at least 100 limbs with CLI. Limbs with CLI may be included as a subset of limbs with PAD. A minimum of 250 patients (400 limbs) and maximum of 400 patients will be enrolled in the study.

7. Statistical Methods

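### The primary CLI endpoint is stricter than the pilot definition behind its planning figures, and limbs meeting only a wider description of CLI count as CLI-negative in the primary ROC

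*SAP*

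**What the plan says.** Both documents define the CLI endpoint in the same words (Protocol and SAP, Section 4.1.1.1.1): "A positive diagnosis of CLI will be defined by exhibition of chronic rest pain and active wounds, verified by" TBI < 0.3. As written, all three conditions must be met.

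The sample-size text (Protocol 12.1.1, SAP Section 6) describes the pilot differently: "CLI (estimated as having a Rutherford category of ≥ 4) occurred in 15% of limbs". No TBI condition is given. For the claudication and CLI curves it adds: "The resulting area under the curve (AUC) for these ROC curves was 0.67 and 0.80, respectively". The group sizes are "84 vs. 22, respectively". The plan then allows for uncertainty in the CLI AUC, "and ± 0.2 of the CLI group, an estimate for the necessary sampling size can be determined", and sets 160 control limbs and at least 100 CLI limbs.

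The background sections of both documents describe CLI more broadly still, as "any patient with chronic ischemic rest pain, ulcers, or gangrene attributable to objectively proven arterial occlusive disease".

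Four further statements decide what happens to a limb on which these descriptions disagree:

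- SAP 7.1.3 puts all participants in every analysis.
- SAP 7.12 classifies patients by Section 4.1.1.1.1 whatever cohort they joined.
- Protocol 12.1.2 treats the ROC outcome as CLI true or false.
- Protocol 8.1 and SAP 5.3 continue enrolment until more than 100 CLI limbs have been measured, without saying which definition counts.

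**The concern.** The reference standard of a primary endpoint differs from the one behind its planning figures. Two consequences follow.

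First, a limb with TBI < 0.3 and rest pain but no wound, or a wound but no rest pain, is labelled CLI-negative, although the background would call it CLI if occlusive disease is proven. If such limbs resemble CLI limbs on the device, the negative group is contaminated. The AUC, sensitivity, specificity and accuracy in SAP 7.10.1 all use these labels.

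Second, the 15% rate, the AUC of 0.80 and the 100-limb target may not describe the group that the endpoint defines. SAP 7.10.1 calls the device predictive of CLI if the 95% CI of the AUC excludes 0.5 at all three visits, so the number of endpoint-positive limbs matters.

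**Working it through.** **1. The wordings side by side**

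| Place | Clinical condition | TBI condition |
|---|---|---|
| Endpoint (both documents, 4.1.1.1.1) | rest pain and wounds | < 0.3 |
| Pilot (Protocol 12.1.1, SAP 6) | Rutherford 4 or higher | none |
| Background (both documents) | rest pain, ulcers or gangrene | none |

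The added TBI condition makes the endpoint differ from the pilot however the word *and* is read.

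**2. The planned 100 CLI limbs.** The documents give neither formula nor sidedness. I assumed a two-sided 0.05 test of AUC 0.5, power 0.80, the lower-bound AUC 0.80 − 0.20 = 0.60, and R = 160/100 = 1.6 controls per case. The Obuchowski variance is

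V = 0.0099 × exp(−a²/2) × [(5a² + 8) + (a² + 8)/R], with a = 1.414 × z(AUC).

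- AUC 0.50: a = 0, V₀ = 0.0099 × (8 + 5) = 0.1287
- AUC 0.60: a = 0.358, V₁ = 0.1274
- n = [1.96√0.1287 + 0.8416√0.1274]² / 0.10² = 100.7

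This matches the stated 100. The same formula at AUC 0.80 gives 10.5 limbs, so the target appears to rest on 0.80 less 0.20. The 15% rate is not needed to obtain it.

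**3. Power if the quota is counted by Rutherford category.** Let f be the share of such limbs that meets the endpoint. The documents do not give f; I assumed 0.25–0.75. With Hanley–McNeil standard errors, power = Φ(0.10/SE − 1.96) at AUC 0.60 against 160 controls.

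| Endpoint-CLI limbs | SE | Power |
|---|---|---|
| 100 (f = 1) | 0.0365 | 0.78 |
| 75 | 0.0404 | 0.70 |
| 50 | 0.0473 | 0.56 |
| 25 | 0.0636 | 0.35 |

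The Obuchowski variance gives 0.80, 0.72, 0.59 and 0.38. If the quota is counted by the endpoint wording, the first row applies at baseline and there is no loss.

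**4. Dilution of the AUC.** Suppose the true AUC is 0.80 against correctly labelled negatives and k = 100 − 100f limbs are misplaced. As a worst case, the device cannot separate them from endpoint-CLI limbs (AUC 0.5).

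- Negatives are 160 healthy limbs plus k: AUC = (160 × 0.80 + 0.5k)/(160 + k). For k = 25, (128 + 12.5)/185 = 0.76; for k = 75, (128 + 37.5)/235 = 0.70.
- With the other 240 − 100 = 140 PAD limbs added, also at 0.80: AUC = (300 × 0.80 + 0.5k)/(300 + k). For k = 25, 252.5/325 = 0.78; for k = 75, 277.5/375 = 0.74.

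In the least favourable case (AUC 0.704, 25 CLI limbs, 235 negatives) SE = 0.0605. Power to exclude 0.5 is Φ(0.204/0.0605 − 1.96), about 0.92.

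These are baseline figures. The healthy cohort is measured once, and the SAP does not say which negatives enter the CLI ROC at 3 and 6 months.

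**5. The pilot CLI group.** 15% of 100 limbs is 15, but the CLI group size is given as 22. The documents therefore do not show beyond doubt that the 0.80 was obtained under the Rutherford definition.

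**The case against.** The strongest reply is that the only operational definition of CLI in either document is Section 4.1.1.1.1, and the SAP classifies by it. Read that way, enrolment continues until more than 100 endpoint-CLI limbs are measured and the planned number is protected. This is a fair reading, and it removes the baseline power loss. It does not change the labels of limbs with one feature, nor the origin of the planning figures.

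The sample-size text also speaks of separating disease groups from healthy controls. If that were the CLI comparison, the intermediate limbs would drop out and would not dilute anything. The analysis section never restricts the comparison in this way, and SAP 7.1.3 points to all participants. The gap needs closing either way.

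The background is a general description taken from the literature, and the pilot definition is called an estimate. A reader might infer that the plan contains three competing study definitions. That goes too far: the mismatch that matters statistically is pilot against endpoint.

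Finally, how many limbs in Rutherford category 4 or higher have only one feature depends on the scale, which the available text does not spell out. The 25–75% range is an assumption.

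**Conclusion.** The concern holds as an inconsistency in the reference standard. The endpoint adds conditions that the pilot definition lacked. The CLI-negative group, as the SAP builds it, can contain limbs that the documents elsewhere describe as CLI. The planning figures are not shown to apply to the endpoint.

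The size is conditional. Power of 0.35–0.70 instead of 0.78 requires that the quota be counted by Rutherford category, that 25–75% of those limbs meet the endpoint, and that the true AUC be 0.60. An AUC of 0.70–0.78 in place of 0.80 requires the same assumed share and that misplaced limbs look exactly like CLI limbs on the device.

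A reader might infer that the CLI analysis is underpowered, or that its AUC will certainly be diluted. The documents support neither: they do not say how the quota is counted, who the negatives are, or what share of limbs is affected. If the true AUC is 0.80, the rule of excluding 0.5 is still met with probability of about 0.92 or more at a single visit. The firmer risk is then bias in the reported accuracy measures. The point should be settled before analysis.

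**What to change.** - Reconcile the CLI wording between the endpoint, the enrolment quota and the sample-size text before analysis. Which clinical definition is right is for the sponsor and investigators to settle.
- State which definition counts towards the 100 limbs, and which limbs form the CLI-negative group at each visit.
- Add a CLI ROC at each visit using Rutherford category 4 or higher alone, which is the pilot definition. Label any version that adds TBI < 0.3 as a separate definition.
- As a sensitivity analysis beside the all-limbs result, report the CLI ROC with limbs that meet only the wider definition left out of the negatives.
- If the endpoint wording is kept, say in the sample-size section that the 15% rate, the AUC of 0.80 and the 100-limb figure derive from a different definition, and explain the pilot group sizes of 15 and 22.

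The cost is SAP wording and one or two extra ROC analyses per visit. Rutherford category, wound inspection and TBI are already collected (Protocol 9.2 and 9.5.3). Leaving out intermediate limbs can flatter the AUC, so that analysis should not replace the all-limbs result.

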4.1.2 Secondary Objectives

The secondary objectives seek to discover the relationship between FlowMet-R measurements and several additional metrics important in vascular medicine. First, the capability of FlowMet-R in the prognosis of requiring a vascular intervention or amputation within three and six months following initial visit will be determined. Additionally, the correlation between FlowMet-R measurements and peripheral artery stenosis will be investigated. Finally, the correlation between changes in ABI/TBI/Rutherford Classification and changes in FlowMet-R data between any two time points will be assessed.

4.1.2.1 Secondary Endpoints

- Utilize FlowMet-R data to create a predictive model for the prognosis of vascular intervention within a three and six month timeframe from initial visit.
- Employ the predictive model of PAD severity to generate an ROC curve for diagnosis of significant stenosis (>50%) in the iliac, femoral, popliteal, peroneal, or tibial arteries.
- Conduct a correlation test between the predictive model of PAD severity and greatest percent stenosis in the iliac, femoral, popliteal, peroneal, or tibial arteries.
- Conduct a correlation test between changes in the predictive model of PAD severity and corresponding changes in ABI, TBI, and Rutherford Classification between any two study time points.

5. Investigation Plan

This study is a non-randomized, multi-center, longitudinal study of healthy subjects and subjects with PAD who are scheduled for ABI, TBI, and either Duplex ultrasound or Angiographic assessments in a vascular clinic. Subjects will first be evaluated for study inclusion/exclusion. If the subject meets the inclusion criteria and wishes to enroll in the study, they will be asked to sign an informed consent form (ICF) and considered for enrollment. If the subject meets inclusion criteria and is enrolled, the subject will undergo approximately 3 minutes of FlowMet-R blood flow measurements in addition to their routine standard of care examination.

Subjects enrolled in the PAD cohort will be assessed according to Event Schedule A in the clinical investigation protocol (CIP) at approximately 0, 3 months, and 6 months. Subject follow ups must meet the scheduled time window within +/- 30 days. Subjects that require a vascular (re)intervention for PAD-related treatment before the final measurement (6 month follow up) will have pertinent data collected and saved in the study registry. The vascular procedure may change the timing with respect to the amount of months after baseline that the follow up visits occur. In that case, the standard of care follow up visits post intervention will be adhered to, and data will be collected from the follow up visits that correspond most closely to timepoints at 3 and/or 6 months post baseline visit.

Subjects enrolled in the Healthy cohort will be assessed according to Event Schedule C in the CIP at a single time point. Imaging outside standard of care will not be performed on the healthy subjects, and healthy cohort subjects with normal ABI and TBI values will be assumed not to have significant peripheral arterial stenosis.

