12.1.3 Analysis of Stenosis

For each artery measured using duplex ultrasound or arterial angiography, the ratio of the PSV distal to the most prominent stenosis to the PCV proximal to the stenosis will be computed (if applicable). The percent stenosis in such arteries will be computed two ways: (1) Percent stenosis = $PSV_{distal}/PSV_{proximal}$, or (2) using the diameter reduction value from Table 3, reprinted from [35].

	Diameter reduction	Waveform	Special broadcasting	PSV distal/PSV proximal
Normal	0	Triphasic	Absent	+++ No change
Mild	1%–19%	Triphasic	Present	<2:1
Moderate	20%–49%	Biphasic	Present	<2:1
Severe	50%–99%	Monophasic	Present	>2:1*

PSV, Peak systolic velocity.

* > 4:1 suggests >75% stenosis, >7:1 suggests > 90% stenosis.

Table 3: Criteria for determining arterial stenosis using peak systolic velocity (PSV) measurements.

Classification of the percent stenosis or presence of greater than 50% stenosis for each limb (used to generate corresponding ROC curve or correlation coefficient) may be determined by either considering a single artery of interest or by considering the artery in each limb with the greatest percent stenosis.

13. Ethics

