5.3 Study Population

Subjects shall be enrolled until the following number of limbs have been measured:

- 160 control limbs (no diagnosed PAD)
- 240 limbs with PAD
 - Of the limbs with PAD, a subset >100 limbs with CLI
 - Of the limbs with PAD, a subset >54 limbs without CLI

Any patient being seen for diagnosis of suspected PAD may be screened for enrollment in the PAD cohort. For patients undergoing intervention, supplemental data will be taken within a catheterization laboratory. Control data from a healthy cohort will also be gathered. Recruitment of healthy subjects is at the site's discretion. Third party recruitment services such as researchmatch.org may be used.

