7.10.2 Secondary Objectives

The secondary endpoints will be analyzed as follows:

1. The capability of the acceleration time from the FlowMet-R device to predict a vascular intervention or amputation will occur within three and six months following initial visit will be determined using the AUC from an ROC curve where the endpoint is vascular intervention or amputation within 7 months, which is the end of the 6 month follow-up window. The 95% CI of the AUC will be derived using the method described in DeLong, et al (1998) [15].
2. The capability of the acceleration time from the FlowMet-R device to predict a $\geq 50\%$ stenosis determined using the AUC from an ROC curve where the endpoint is vascular intervention or amputation within 7 months, which is the end of the 6 month follow-up window. The 95% CI of the AUC will be derived using the method described in DeLong, et al (1998) [15].
3. The correlations between the acceleration time from the FlowMet-R device and peripheral artery stenosis, changes in ABI, and changes in TBI will be computed using Pearson correlations. The changes for ABI and TBI will be as follows: 0 to 3 months, 0 to 6 months, and 3 to 6 months.
4. The correlation between the acceleration time from the FlowMet-R device and changes in Rutherford Classification will be computed using the Spearman correlation. The changes for Rutherford Classification will be as follows: 0 to 3 months, 0 to 6 months, and 3 to 6 months.

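### The cut-off for a stenosis-positive limb is >50% in the endpoint but ≥50% in the SAP analysis, and no rule says how a limb graded only as Severe (50%–99%) is classed

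*SAP*

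**What the plan says.** Four places fix or use the cut-off.

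- SAP 4.1.2.1 sets the endpoint: "generate an ROC curve for diagnosis of significant stenosis (>50" per cent). Protocol 4.1.2.1 has the same strict inequality.
- Protocol 12.1.3, on deriving the limb-level value, is also strict: "Classification of the percent stenosis or presence of greater than 50% stenosis for each limb".
- SAP 7.10.2 item 2, which analyses this endpoint, is inclusive: "to predict a $\geq 50\%$ stenosis determined using the AUC from an ROC curve".
- The criteria table in Protocol 12.1.3 gives diameter reduction in bands: Moderate 20%–49%, Severe 50%–99%. A footnote refines Severe only for velocity ratios above 4:1 (more than 75%) and above 7:1 (more than 90%).

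Protocol 12.1.3 allows two ways of obtaining percent stenosis. The second is "using the diameter reduction value from Table 3, reprinted from [35"], the table just described.

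SAP 7.12, the section for changes to the planned analysis, lists only the classification of patients regardless of enrolment cohort. It does not mention the stenosis cut-off.

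**The concern.** The cut-off defines the positive class of a named secondary ROC curve. Two inequalities are written for it, and nothing shows that the difference was intended. The analyst must choose one, and with no rule fixed in advance that choice could be made after the data are seen.

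On a finely measured continuous scale, > against ≥ would hardly matter. Here the protocol permits a banded scale whose upper band begins exactly at the disputed value, so the strict rule does not line up with the table that supplies the data.

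**Working it through.** There is no stated figure to reproduce, so the check applies each written rule to values around the boundary.

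| Recorded stenosis | Rule >50% | Rule ≥50% | Table band in Protocol 12.1.3 |
|---|---|---|---|
| 49% | negative | negative | Moderate |
| 50% | negative | positive | Severe |
| 51% | positive | positive | Severe |
| Band only, 50%–99% | not determined | positive | Severe |

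The two inequalities disagree at exactly 50% and nowhere else. The last row is a different problem. Every value in the band satisfies ≥50%, so the inclusive rule settles it. The strict rule does not, because the band contains 50.

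**How a band-only record could arise.** Protocol 9.7.4 lists the duplex entries for the case report form as the location of maximum stenosis, the velocities on either side of it and the waveform shape. It does not list a percentage. A percentage is then derived under 12.1.3. With the table method, a ratio above 2:1 and not above 4:1 yields only the 50%–99% band.

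**Which limbs could be involved.** SAP section 5 assumes that healthy-cohort subjects with normal ABI and TBI have no significant stenosis, so their limbs do not depend on the cut-off. Protocol 9.7.4 requires duplex, or angiography if duplex is unavailable, for PAD and CLI limbs. The natural denominator is the planned "240 limbs with PAD" in SAP 5.3.

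**Size.** The share of limbs recorded at exactly 50% is not in the documents. For an assumed share f, the number that change class is 240 × f:

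- f = 0%: 0 limbs
- f = 2%: 240 × 0.02 = 4.8, about 5 limbs
- f = 5%: 240 × 0.05 = 12 limbs
- f = 10%: 240 × 0.10 = 24 limbs
- f = 20%: 240 × 0.20 = 48 limbs

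These shares only show the scale. None is supported by the text, and zero is as admissible as any other.

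**The case against.** The strongest reply is that the mismatch has little practical reach.

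- A limb changes class only if its greatest stenosis, or that of the single artery of interest (Protocol 12.1.3 allows either), is exactly 50%. Under the greatest-stenosis option, a 50% lesion beside a worse one changes nothing.
- For duplex, the table separates Moderate from Severe by a velocity ratio below or above 2:1. The wording of the percentage cut-off does not alter that velocity rule.
- SAP 7.2 says the objectives are not hypothesis-driven and are presented descriptively, and SAP 7.10.2 sets no success criterion for this analysis.
- Two other faults in the same texts are larger. SAP 7.10.2 item 2 goes on to name vascular intervention or amputation within 7 months as the ROC endpoint, so read literally its outcome is not stenosis. The first method in Protocol 12.1.3 sets percent stenosis equal to the distal-to-proximal velocity ratio, so an unchanged velocity (ratio 1) reads as 100% and a 2:1 ratio as 200%. On that scale a cut at 50% means little under either inequality.

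All of this stands as a limit on importance. It does not remove the contradiction. Correcting item 2 means writing the stenosis outcome into it, and the inequality must then be settled.

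A reader might infer more: that because the table gives bands, 50% is a common recorded value, and that every Severe limb without a ratio above 4:1 would switch. The documents do not support this. A band is not a recorded 50%. The switch would need a rule that stores Severe at its lower edge, and neither document contains one. The natural reading is that a Severe-band limb is positive under either wording. Angiography could give an exact 50%, but the documents do not say how such values are recorded.

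**Conclusion.** The inconsistency is real and undeclared: strict in Protocol 4.1.2.1, Protocol 12.1.3 and SAP 4.1.2.1, inclusive in SAP 7.10.2 item 2. The analysis cannot be programmed from the text without choosing between the two. The strict version also leaves a Severe-band record without a defined class.

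The effect on results cannot be computed and may be near zero. It is confined to limbs recorded at exactly 50%, plus limbs known only by the Severe band if no rule is written for them. No primary endpoint is touched. This is a minor correction, worth making because it is cheap and because the SAP sentence concerned has to be rewritten anyway.

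**What to change.** Before analysis, in one SAP edit:

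1. State a single inequality in SAP 4.1.2.1 and in SAP 7.10.2 item 2.
2. State that any limb in the Severe band of the Protocol 12.1.3 table is stenosis-positive. Of the two inequalities, ≥50% is the one that matches that band. If >50% is kept, this rule is still needed for band-only records. Cite the table by section, since Protocol 9.3 also has a Table 3.
3. Replace the outcome in item 2, now intervention or amputation within 7 months, with the stenosis outcome.
4. If ≥50% is chosen, record it in SAP 7.12 as a change from the protocol, and align Protocol 4.1.2.1 and 12.1.3 at the next amendment.

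The cost is small: a SAP edit and, if ≥50% is chosen, a declared departure from the protocol wording. It is not purely a matter of wording on the protocol side, because Protocol 14.6 sends revisions to all affected IRBs and requires approval before a site implements them. That is why the protocol text can wait for the next amendment.
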